10.2 Risk Minimization

Refer to "Prevention and Mitigation" column in the table under **Section 10.1**.

10.3 Potential Benefits

The objective of this study is to evaluate the safety and performance of the MiniMed 780G system, it is anticipated that the system will allow improved glycemic control in the selected population of young patients in MDI or CSII with or without CGM.

Currently MiniMed 780G pump use is approved for subject older than 7 years old so the study will give the opportunity for subjects, ages 2-6 to have access to this system used both in Manual and Auto Mode during the study.

The information gathered in this study will help to extend labeling for MiniMed 780G system and the data collected in the study might help the patients and physicians determine the best treatment options in the future.

CIP342 Clinical Investigation Plan Page 63 of 96 Mectronic D00674412 Version E Page 63 of 96 Mectronic

10.4 Risk-Benefit Rationale

The main benefit of this study is that paediatric subjects (2-6 years old) may experience improved glucose control, due to the fact that the participants will be followed with higher frequency of visits, which will allow closer medical follow-up when compared to standard of care.

Parents/legal guardians of the subject may also increase their understanding of the disorder.

Risks related to the pump delivering too much or not enough insulin are minimized through a variety of safety checks that are an integral part of the MiniMed 780G closed loop algorithm.

11 Adverse Events

11.1 Adverse Events

Throughout the course of the study, investigational centers will make all efforts to remain alert to possible reportable adverse events (AEs) or untoward findings. The study personnel will elicit reports of AEs from the subject at each visit (including phone calls) starting at the time of signing the informed consent documenting the medical diagnosis, date of event start and end, causality (relationship to device or procedure), treatment, outcome, assessment of seriousness, and description that includes the details of the event.

11.2 Definitions and Classification of Adverse Events

All adverse events (including non-subject AEs) will be collected and classified by using the ISO 14155:2020 definitions, as defined below. Where the definition indicates "device", it refers to any device used in the study. This might be the device under investigation, or any market released component of the system.

Severe Hypoglycemia is an event requiring assistance of another person due to altered consciousness to actively administer carbohydrate, glucagon, or other resuscitative actions. This means that the subject was impaired cognitively to the point that he/she was unable to treat himself or herself, was unable to verbalize his or her needs, and was incoherent, disoriented and/or combative.

These episodes may be associated with sufficient neuroglycopenia to induce seizure or coma. Plasma glucose measurements may not be available during such an event, but neurological recovery attributable to the restoration of plasma glucose to normal is considered sufficient evidence that the event was induced by a low plasma glucose concentration.⁴

Diabetic Ketoacidosis/DKA diagnostic criteria: BG greater than (>) 250 mg/dL or greater than (>) 13.9 mmol/L, arterial pH less than (<) 7.3, bicarbonate less than (<) 15 mEq/L, moderate ketonuria or ketonemia and requiring treatment within a health care facility.⁵

Hyperglycemic events will be recorded as DKA if the event includes the presence of all of the following:

- Arterial blood pH less than (<) 7.30 or serum bicarbonate less than (<) 15 mEq/L
- Blood glucose greater than (>) 250 mg/dL or greater than (>) 13.9 mmol/L

- Serum ketones or large/moderate urine ketones
- Symptoms such as polyuria, polydipsia, nausea, or vomiting
- Treatment provided in a health care facility

Adverse Event (AE) (ISO 14155:2020)

Untoward medical occurrence, unintended disease or injury, or untoward clinical signs (including abnormal laboratory findings) in subjects, users or other persons, whether or not related to the investigational medical device and whether anticipated or unanticipated.

Note 1 to entry: This definition includes events related to the investigational medical device or the comparator.

Note 2 to entry: This definition includes events related to the procedures involved.

Note 3 to entry: For users or other persons, this definition is restricted to events related to the use of investigational medical devices or comparators.

Adverse Device Effect (ADE) (ISO 14155:2020)

Adverse event related to the use of an investigational medical device.

Note 1 to entry: This definition includes adverse events resulting from insufficient or inadequate instructions for use, deployment, implantation, installation, or operation, or any malfunction of the investigational medical device.

Note 2 to entry: This definition includes any event resulting from use error or from intentional misuse of the investigational medical device.

Note 3 to entry: This includes 'comparator' if the comparator is a medical device.

Serious Adverse Event (SAE) (ISO 14155:2020)

Adverse event that led to any of the following

- a) death,
- b) serious deterioration in the health of the subject, users, or other persons as defined by one or more of the following:
 - 1. a life-threatening illness or injury, or
 - 2. a permanent impairment of a body structure or a body function including chronic diseases, or
 - 3. in-patient or prolonged hospitalization, or
 - 4. medical or surgical intervention to prevent life-threatening illness or injury or permanent impairment to a body structure or a body function,

CIP342 Clinical Investigation Plan Page 65 of 96 Medtronic D00674412 Version E Page 65 of 96 Medtronic

c) foetal distress, foetal death or a congenital abnormality or birth defect including physical or mental impairment

Note 1 to entry: Planned hospitalization for a pre-existing condition, or a procedure required by the CIP, without serious deterioration in health, is not considered a serious adverse event.

Serious Adverse Device Effect (SADE) (ISO 14155:2020)

Adverse device effect that has resulted in any of the consequences characteristic of a serious adverse event

Unanticipated Serious Adverse Device Effect (USADE) (ISO 14155:2020)

Serious adverse device effect which by its nature, incidence, severity or outcome has not been identified in the current risk assessment.

Note 1 to entry: Anticipated serious adverse device effect (ASADE) is an effect which by its nature, incidence, severity or outcome has been identified in the risk assessment.

Serious Health Threat (ISO 14155:2020)

Signal from any adverse event or device deficiency that indicates an imminent risk of death or a serious deterioration in the health in subjects, users or other persons, and that requires prompt remedial action for other subjects, users or other persons

Note 1 to entry: This would include events that are of significant and unexpected nature such that they become alarming as a potential serious health hazard or possibility of multiple deaths occurring at short intervals.

11.3 Recording of Adverse Events

The investigator or designee will record ALL AEs and DDs while the subject is enrolled in the clinical study (Refer to **Section 13** for DD reporting).

Each AE needs to be assessed for its device or procedure relatedness. A device related AE is associated with the use of the study device (e.g., infection of sensor site or infusion set occlusion resulting in DKA). A procedure related AE is associated with testing related to the study procedures specified in the CIP (e.g., needle (blood draw) insertion pain).

Examples of device or procedure related AEs include:

- *Device* related (ADE): insertion site infection
- Serious adverse *device effect*: cellulitis at device insertion site requiring hospitalization
- Procedure related AE: bruising at needle (blood draw) insertion site

CIP342 Clinical Investigation Plan			
D00674412	Version E	Page 66 of 96	Medtronic

An outside standard of care CIP procedure related AE in this study is associated with a study procedure that is required per the study protocol and is in addition to the standard of care for the device (see Study Design under **Section 9**).

Subjects participating in the study have diabetes and are expected to experience hypoglycemia and or hyperglycemia. These normal events are not expected to be reported to sponsor as this is not considered an untoward event, but rather an expected occurrence. Any glycemic excursion that meets the protocol definition of severe hypoglycemia or DKA is considered an untoward event and a worsening from the subject's baseline and would be reported to sponsor on an AE eCRF.

Baseline medical conditions should only be reported to sponsor on an AE eCRF if there is a worsening from the subject's baseline. For example, a subject previously diagnosed with asthma is hospitalized for severe asthma attack would be a reportable event.

Adverse events will be documented in the subject source file and reported to sponsor on an eCRF. The investigational center is responsible for documentation of AEs including obtaining source documents related to the event, such as emergency medical technician/paramedic reports, hospital records (admission summary; lab results, test results, discharge summary) or device uploads to support the event. Source documents will be reviewed to determine if additional AEs have occurred and require reporting.

Adverse events that have not resolved at the time of the subject's discontinuation or completion of the study should have an "outcome" of Not Recovered/Not Resolved at study end in subject source and on an eCRF. The investigator should ensure that subject is aware of any follow-up or additional treatment that is required for any ongoing AE at EOS participation; however, there will be no eCRF entry for the ongoing follow-up.

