9.8 Subject Exit, Withdrawal or Discontinuation

Subjects and/or their parent/legal guardian may choose to withdraw from the study at any time by notifying investigational center staff of their intent.

Whenever possible, the investigational site staff will perform an Early Termination visit when a subject decides to withdraw from the study early or if the subject is withdrawn early upon decision of the investigator or sponsor (during a normal study visit or an unscheduled visit) (described in **Section 9.1**). If a subject chooses to end his or her study participation or if the subject is removed from the study at the Investigator's discretion or for failure to meet the study requirements, the reason for withdrawal must be documented. All study devices and supplies must be returned (as applicable) and documented both in source documents and on an eCRF. Following study exit, withdrawal or discontinuation subjects will receive standard medical care from their own providers.

A subject will be withdrawn from the study if:

- In the opinion of the investigator, the subject's health or safety would be compromised by continuing in the study (e.g., infection at skin site, severe skin reaction to adhesive).
- In the opinion of the investigator, it is in the subject's best interest to discontinue participation in the study.
- During the course of the study, subject is taking oral, injectable, or IV glucocorticoids
- During the course of the study, subject begins participation in another investigational study (drug or device).

Documentation of the reason(s) leading to subject withdrawal will be kept in the subject's source documentation.

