11.4 Notification of Adverse Events

Sponsor Notification:

The investigational center staff must report all AEs to Medtronic in a timely manner. All severe hypoglycemia, DKA, SAE, SADE, and DD with SADE potential should be reported immediately to Medtronic (but not later than 72 hours). For the previously mentioned events, the AE eCRF will be completed with all known details as soon as possible, this will serve as notification to Medtronic. If the study database cannot be accessed due to technical problems, contact the sponsor via email at [contact] and provide the de-identified known details of the event. Once the access issue has been corrected, the event should be entered onto an AE eCRF.

Source documents that support the event (e.g., clinic notes, hospital admission and discharge records, lab reports, EMT reports, ER/Urgent Care) should be provided to the sponsor via Medtronic's secure upload application. All source documents/medical records should be redacted of patient identifiers (full name, address, etc.) prior to providing to the sponsor. Each source page should be identified with the subject ID.

CIP342 Clinical Investigation Plan			
D00674412	Version E	Page 67 of 96	Medtronic

Table 8. Investigator Reports to Sponsor

Event 1	Type To Report	Timeframe for Reporting
•	Serious Adverse Device Effect (SADE)	
•	Unanticipated Serious Adverse Device Effect (USADE)	Immediately, but no later than 72 hours after
•	Serious Adverse Event (SAE)	investigational site study personnel's awareness
•	Adverse Device Effect (ADE)	of the event (or sooner if required by local
•	Device Deficiency that might have led to a SADE (see	regulation)
	Section 13)	
•	Adverse Event (AE)	In a timely manner from the investigator's /
•	Device Deficiency (DD) (see Section 13)	site's first knowledge of the event

Sponsor Reports:

Regulatory reporting of AEs and DDs will according to local regulatory requirements.

In countries following EU MDR 2017/745, AEs will be reported according to EU MDR 2017/745 Art. 80(2) and Medical Device Coordination Group (MDCG) 2020-10/1 guidance and additional local requirements if applicable.

In accordance with EU MDR Art. 80(2) the following events are considered reportable:

- a) any serious adverse event that has a causal relationship with the investigational device, the comparator or the investigation procedure or where such causal relationship is reasonably possible;

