- b) any device deficiency that might have led to a serious adverse event if appropriate action had not been taken, intervention had not occurred, or circumstances had been less fortunate;
- c) any new findings in relation to any event referred to in points a) and b).

Table 9. Sponsor Adverse Events Reporting Requirements to National Competent Authority

Events To Report in EU/EEA	Reporting Requirements and Timeframe
 Any device and/or procedure related Serious Adverse Events (SAE) and/or Device Deficiency (DD) that may have led to a SADE which indicates an imminent risk of death, serious injury, or serious illness and that requires prompt remedial action for other patients/subjects, users or other persons or a new finding to it (occurred in the study under same CIP) 	Immediately, but no later than 2 calendar days after awareness by sponsor of a new reportable event or of new information in relation with an already reported event
 Any device and/or procedure related SAE and DD that may have led to an SADE (occurred in the study under same CIP*) – including updates 	Immediately, but not later than 7 calendar days after awareness
Events To Report in UK	Reporting Requirements and Timeframe

D00674412	Version E	Page 68 of 96		Medtronic
 Any SAE and/or DD that may hav which indicates an imminent risk injury, or serious illness and that remedial action for other patients or other persons or a new finding in the study under same CIP) 	e led to a SADE of death, serious requires prompt /subjects, users g to it (occurred	Immediately, but no later than awareness by sponsor of a new of new information in relation reported event	2 calenda reportal with an	ar days after ble event or already
 Any SAE and DD that may have (occurred in the study under sar including updates 	ed to an SADE ne CIP*)–	Immediately, but not later tha after awareness by the sponse reportable event or of new info with an already reported event	n 7 cale or of the ormation t	ndar days new in relation
 All SAEs 		Quarterly report according to C objection'. Quarterly after CA a	CA `letter approval	of no date

In addition, it is the responsibility of the investigator and the sponsor to abide by the AE reporting requirements stipulated by local law and the study site's EC.

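### Section 11.3 bars eCRF follow-up of adverse events open at exit, with no exception for serious or device-related events, so outcomes are lost and a later upgrade to serious could go uncounted

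*Protocol*

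**What the plan says.** **Recording.** Protocol 11.3 tells the investigator to "record ALL AEs and DDs while the subject is enrolled in the clinical study". An event that is open when the child discontinues or completes gets the outcome "Not Recovered/Not Resolved at study end in subject source and on an eCRF". The investigator makes sure that the family knows what further care is needed; "however, there will be no eCRF entry for the ongoing follow-up". Seriousness and device relationship make no difference to this rule.

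**Notification.** Under Protocol 11.4, for severe hypoglycaemia, DKA, SAEs, SADEs and deficiencies with SADE potential, "the AE eCRF will be completed with all known details as soon as possible, this will serve as notification to Medtronic". Supporting papers travel separately by secure upload: "hospital admission and discharge records, lab reports, EMT reports, ER/Urgent Care) should be provided to the sponsor".

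**Updates to authorities.** The same section lists as reportable "any new findings in relation to any event referred to in points a) and b", and Table 9 extends the deadlines to updates.

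**Withdrawal.** Section 9.8 withdraws a child when the investigator judges that continuing would compromise health or safety. Its examples are "infection at skin site, severe skin reaction to adhesive".

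**Analysis.** SAE, SADE and USADE counts are safety endpoints (Protocol 4.4, SAP 4.3), reported by period and treatment (SAP 7.10.3). The SAP has no rule for an event that becomes serious after exit.

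**The concern.** Whether an event is serious often depends on what happens next, such as an admission or a life-threatening course. A rule that ends data entry at exit is usually harmless for minor events. Here it also covers the events that can themselves cause the exit, so the child may leave the dataset while the device event is still active.

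Two things are at stake. One is the outcome of serious events, which a reader of the safety report will want. The other is the completeness of the serious-event counts for devices that are investigational in children aged 2 to 6, including non-CE-marked products in arm A2. A post-exit upgrade that is missed can only lower those counts. The data monitoring committee also reviews rates of SAEs and device-related events (Protocol 12.2).

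**Working it through.** No arithmetic applies, because the plan states no figure that depends on this rule. The check is to follow an open event through the written procedures.

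**1. When exit happens.** Study-phase completers do not exit at Visit 11; they move into the continuation phase (Protocol 8.5.2), where recording goes on. Exit is at Visit 15 or at early termination (9.8.1). Both visits include an adverse event review (9.1, 9.1.3). After that the child returns to routine care.

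**2. Event already serious at exit.** It is on the form and in the count. Under 11.3 its later course is not entered, so the final outcome is missing. The count is unaffected.

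**3. Event non-serious at exit.** The protocol's own examples describe the path. Section 11.3 gives an insertion site infection as a device-related adverse event, and gives "cellulitis at device insertion site requiring hospitalization" as a serious adverse device effect. Suppose a child is withdrawn under 9.8 with such an infection, is reviewed at the early termination visit, and is later admitted. The written routes that might pick up the change are these:

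- **AE eCRF (11.3, 11.4).** Recording is tied to enrolment, and follow-up entries are excluded.
- **Clinical events committee (12.1).** The form is updated if the investigator accepts the committee's view. However, the events listed for review are SAEs, SADEs, USADEs, severe hypoglycaemia and DKA. A non-serious device event is not on the list.
- **Sponsor safety query (11.5).** This starts when an event is received and checks its completeness and accuracy. It is not post-exit follow-up.
- **Source document upload (11.4).** This supports an event that has been reported. Nothing asks for records of its course after exit.
- **Update reports (11.4, Table 9).** The deadlines run from awareness, and no post-exit step is defined that would create awareness.

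None of these is a planned step that captures the upgrade.

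**4. Analysis side.** Protocol 14.1 draws data from eCRFs and device uploads up to the end of the study. In SAP 7.2 the last safety window runs from Visit 13 with no upper limit, so a late entry for a child who reached Visit 13 would not be excluded. For a child who leaves earlier, the windows are bounded by visits that may never take place. SAP 7.2 does not say whether an upgraded event belongs to its onset date or its upgrade date. SAP 7.7.1 and 7.7.2 end exposure at study exit.

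**5. Size.** The count could fall short only by non-serious events that are open at exit and become serious later. That number needs an SAE rate, the share of events open at exit, and the rate of later worsening. The documents give none of these.

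**The case against.** The case against is substantial, and several parts of it stand.

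- **The form is not closed.** A reader might infer that 11.3 locks it. The text excludes entries for ongoing follow-up; it does not bar reclassifying an event already recorded. Committee review and sponsor queries have no stated cut-off at exit. This stands.
- **It does not follow that an upgraded event can never be counted.** The reporting clock in Table 8 runs from the site's awareness, with no exit limit, and the last SAP window is open. The documents are silent on post-exit upgrades; they do not prohibit them. This stands, but silence leaves capture to chance.
- **The update reports do not lose their source.** They depend on awareness, source documents reach the sponsor outside the eCRF, and local-law and ethics committee duties apply as well. Section 11.3 governs data capture and 11.4 governs vigilance, so a site can comply with both. This stands as far as it goes. What is missing is a defined step linking the two.
- **The endpoints are numbers of events, not outcomes.** Events serious before exit are counted. This stands and narrows the possible undercount to later upgrades.
- **Ending capture at exit is a legitimate choice, and SAP 7.5.2 plans no test on safety endpoints.** This is fair for minor events. It is weaker for serious and device-related ones, because a device event can be the reason for the exit.

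**Conclusion.** The concern holds in a limited form. Section 11.3 excludes follow-up entries for all open events, and the documents contain no planned step that captures either the final outcome of a serious event open at exit or the upgrade of a non-serious device-related event. The first is a loss of outcome data. The second is a possible undercount of SAEs, SADEs and USADEs, arising only at early termination or Visit 15.

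No size can be given. A reader might start from the planned attrition in the synopsis, 80 randomised less 64 completing the continuation phase, which is 16 children, and apply assumed percentages. That does not work. The 16 is attrition from all causes; it says nothing about events open at exit or worsening afterwards, and it leaves out Visit 15 completers with open events. Nor do the documents show that any loss would differ between treatments.

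The conclusion assumes that sites follow 11.3 as written and do not volunteer post-exit information. Where they do volunteer it, the gap is smaller. The change is still worth making, because it is specific and cheap and concerns safety data in young children.

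**What to change.** **Protocol 11.3.** Reconcile the follow-up rule with the update commitment in 11.4 by adding an exception. For SAEs, SADEs and device-related adverse events unresolved at exit, the site updates outcome and seriousness on the existing AE eCRF until the event is resolved, is stable, or the database is locked, whichever comes first. Other unresolved events stay as now written.

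**SAP 7.10.** Add that an adverse event with onset before exit that becomes serious afterwards is counted as SAE, SADE or USADE in the period of onset and flagged as a post-exit upgrade. The flag is needed for two reasons: exposure ends at exit, so these events arise outside the person-time counted, and early leavers can have a longer interval before database lock in which an upgrade can occur. With the flag, counts can be shown with and without such events.

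**Cost.** Wording changes in two documents, a few contacts with families after exit, and a few forms kept open until the event settles or the database is locked. Visits, treatment and the efficacy analyses do not change.
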